7.3 Exclusion Criteria

Patients must be excluded from participating in this study if they meet any of the following criteria:

- (1) Is pregnant, lactating, is possibly pregnant, or is actively trying to conceive during the study period.
- (2) Is a patient for whom an endoleak or other clinically meaningful EVAR-related complication (as judged by the investigator) has already been discovered.
- (3) Is a patient who is undergoing surveillance following a Thoracic Endovascular Repair (TEVAR).
- (4) Has a known or suspected history of immediate or delayed hypersensitivity (including but not limited to hives, anaphylactoid or cardiovascular reactions, laryngeal edema, and bronchospasm) to iodine or any iodinated contrast medium.
- (5) Is using metformin (e.g., Glucophage®) that cannot be discontinued for the period of 48 hours prior to the Baseline Visit and for at least 48 hours after the imaging procedure (renal function must be evaluated before metformin is resumed).
- (6) Has been exposed to any intravascular iodinated contrast medium in the 14 days prior to the Baseline Visit.
- (7) Has congestive heart failure (New York Heart Association [NYHA] Class IV) or hepatic failure/liver cirrhosis according to the investigator's judgement.
- (8) Has stage V CKD, defined as eGFR <15 mL/min/1.73 m² according to the MDRD equation.
- (9) Has a pre-existing requirement for renal dialysis.
- (10) Has undergone percutaneous transluminal renal angioplasty (PTRA) within 12 months before the index EVAR procedure or is scheduled to undergo PTRA during the study period.
- (11) Has any clinically active, serious, life-threatening disease, medical, or significant psychiatric condition; has a life expectancy of less than 6 months; or is, in the Investigator's opinion, unsuitable for participation in the study for any reason.
- (12) Has been enrolled in another clinical study within the 30 days prior to the Screening Visit or is planned to enroll in another clinical study within the duration of this study.

- (13) Has been previously enrolled in this study.
- (14) Is using i.v. vasopressor or inotropic medications.
- (15) Has used nonsteroidal anti-inflammatory drugs (NSAIDs) or any nephrotoxic medication within 48 hours of the Baseline Visit or will do so within 72 hours after the CT procedure (renal function must be evaluated before any nephrotoxic medication is resumed) – with the exception of acetylsalicylic acid (Aspirin) at a dose of ≤ 100 mg daily (QD).
- (16) Has been hospitalized within 30 days prior to Screening Visit for any reason other than practical purposes for management of tests or diagnostic assessments.

7.4 Withdrawal and Termination Criteria

7.4.1 Patient Withdrawal

There are no formal withdrawal criteria for this study. During the conduct of the study, the Sponsor will review the safety data for trends and signals that would indicate the need for withdrawal of a patient.

In accordance with the Declaration of Helsinki, each patient is free to withdraw from the study at any time. Investigator(s) also have the right to withdraw patients from the study in the event of illness, AEs, or other reasons concerning the health or well-being of the patient, or in the case of lack of co-operation.

Should a patient decide to withdraw after administration of Visipaque™ 320 mg I/mL Injection or saline placebo, or should the Investigator(s) decide to withdraw the patient, all efforts will be made to complete and report the observations up to the time of withdrawal as thoroughly as possible. A complete final evaluation at the time of the patient's withdrawal should be made and an explanation given of why the patient is withdrawing or being withdrawn from the study.

The reason for withdrawal must be noted in the electronic Case Report Form (eCRF). If the reason for withdrawal is a clinical AE, monitoring will continue until the outcome is evident. The specific event or test result(s) must be recorded in the eCRF.

7.4.2 Study or Site Termination

The Sponsor reserves the right to terminate the study at any time. The Sponsor also reserves the right to discontinue participation of a study center at which no patients have been enrolled within 6 months of initiation or in case of safety concerns or major protocol violations.

8 TREATMENT OF PATIENTS

8.1 Investigational Medicinal Product (IMP)

8.1.1 VisipaqueTM Injection

VisipaqueTM (iodixanol) Injection 320 mg I/mL will be used as the contrast agent for the CECT (CTA) examinations performed in this study.

VisipaqueTM Injection 320 mg I/mL is provided as a clear, colorless to pale yellow aqueous solution under secure conditions and must not be frozen. The product must be stored protected from light and must be kept at room temperature, between 15°C to 30°C [59°F to 86°F]. VisipaqueTM Injection 320 mg I/mL should not be refrigerated.

VisipaqueTM Injection 320 mg I/mL will be supplied in 100-mL bottle containers. An “investigational use only” label will be attached to the individual containers and the supply box.

Patients will be dosed with 100 mL VisipaqueTM Injection 320 mg I/mL followed by a 10 mL saline flush to ensure delivery of the full dose of Visipaque in accordance with the protocol and the CT Imaging Manual.

8.1.2 Comparator (Placebo)

The placebo will consist of 100 mL saline to be administered in a single i.v. injection followed by a 10 mL saline flush. The saline will be provided by a central supplier and stored securely at room temperature.

Further details on administration of saline placebo are given in the CT Imaging Manual.

8.1.3 Optical Renal Function Monitoring

A subset of patients (no more than 100), at selected sites in the USA, may also receive an inert fluorescent pyrazine-based tracer agent (MB-102), which is used with an ORFM to enable accurate tracking of kidney function, by non-invasively measuring fluorescent light emission over time. This will be the purpose of a specific amendment to this protocol during the course of the present clinical trial.

MB-102 will be provided directly from MediBeacon (MediBeacon, Saint Louis, MO, USA) and will be administered at the Baseline Visit, 1 hour prior to VisipaqueTM or saline placebo.

Further information regarding MB-102 and ORFM will be provided to the participating study centers as a separate local amendment to this protocol. Specific patient information will be

provided to potential patients and their consent to participate will be documented on an IRB approved Informed Consent Form.

8.1.4 IMP Accountability

Each Investigator is responsible for ensuring that deliveries of Visipaque™, saline placebo and other study materials from the Sponsor are correctly received, recorded, handled, and stored safely and properly in accordance with all applicable regulatory guidelines, and used in accordance with this protocol.

All Visipaque™ and placebo containers (opened, unopened, or empty) must be returned to the Sponsor or destroyed on site after the study and overall drug accountability have been completed by the Sponsor or representative. A list of Visipaque™, placebo and other materials that were returned, or destroyed, must be prepared and signed by the Principal Investigator or designee. If there are any discrepancies, an explanation for these should also be provided.

8.1.5 Registration of Investigational Medicinal Product(s) Complaints

In the event of an IMP complaint (e.g., breakage, leakage, particulate matter, discoloration), the Investigator or recipient of the IMP is requested to report the problem on the relevant shipping documentation (e.g., 'Delivery Note for Product', Drug Shipping and Receiving Form, or equivalent form). This should be promptly forwarded to the person indicated on the shipping documentation. Once received, the Clinical Supplies Manager will register the complaint and determine if the complaint is minor or significant according to Sponsor procedures. All complaints will be followed up and the appropriate action will be implemented according to Sponsor procedures.

8.2 Method of Numbering Patients and Assigning Patients to Treatment Groups

A unique allocation number will be assigned to each patient at a center in successive order of entering the study after signing the informed consent form. No patient may be entered or screened (after failing to meet inclusion/exclusion criteria) into the study more than once. The allocation number will be unique for each patient in the study and will consist of 7 numbers in total: 3 numbers for the center identification and 4 numbers for the patient identification at the center (e.g., 002-0001: first patient in center No. 2).

Once a patient number is assigned, it cannot be reassigned even if the patient is deemed ineligible or withdraws consent. To preserve the scientific integrity of the study, numbers must be assigned in numeric order.

A patient who has given informed consent (or for whom informed consent has been given) but does not fulfil the criteria to participate in the study will receive a patient number and will be logged as a screening failure within the interactive web response system (IWRS)/ interactive

voice response system (IVRS). The patient will also be documented on the Screening Log by using the patient's initials and patient number.

Once patients have completed the screening process they will be enrolled in the study and will be randomly assigned to the NECT group or the CECT group in a 1:1 ratio in accordance with a pre-specified randomization list. Allocation to the enrolment groups, including randomization, will be performed centrally (via the IWRS or IVRS) by the Sponsor or contract research organization (CRO). Randomization will be stratified by CKD stage to achieve a balance of this factor between treatment groups.

No patient will be administered VisipaqueTM or saline placebo before it has been determined that the patient meets the study's inclusion/exclusion criteria and signed and dated informed consent has been obtained.

8.3 Selection of Doses and Timing

Patients randomized to receive VisipaqueTM will be dosed with 100 mL VisipaqueTM Injection 320 mg I/mL followed by a 10 mL saline flush. The size of the saline placebo dose is intended to mimic the size of the VisipaqueTM dose, i.e., 100 mL saline followed by 10 mL saline flush.

The dose of VisipaqueTM or saline placebo will be administered prior to the CT procedure as detailed in the Imaging Manual.

8.4 Blinding

This study is not blinded.

8.5 Prior and Concurrent Medications or Procedures

Any medications taken by the patient, medical procedure, or diagnostic assessment within 14 days before VisipaqueTM or saline placebo administration and up to the end of Follow-Up 3 will be recorded in the eCRF along with the indication for use and dosage. Either the generic or the trade name may be recorded. The Sponsor/CRO will encode all therapy and medication according to a current well-recognized dictionary of medical codes.

Metformin, NSAIDs, and drugs with nephrotoxic potential will be required to be discontinued temporarily per exclusion criteria #5 and #15, and the current use of i.v. vasopressor or inotropic medications is prohibited per exclusion criterion #14. The prophylactic use of acetylsalicylic acid (Aspirin) in a dose of ≤ 100 mg QD is permitted. The use of *N*-acetylcysteine (NAC) is discouraged for the purpose of preventing AKI.

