There is a need to explore the renal safety of the i.v. administration of the iso-osmolar contrast medium iodixanol (Visipaque™ Injection 320 mg I/ml) in patients with chronic renal impairment. Many clinicians have been avoiding the use of iodinated contrast material for patients with kidney disease because of the presumption that these agents pose a risk of nephrotoxicity in patients with compromised renal function. This abundant, but also controversial, literature has led to the avoidance of using i.v. iodinated contrast media in patients with stages III and IV CKD because of the continued fear of inducing CIN. Even when rigorous hydration protocols and concomitant pre-medication are used in an attempt to prevent CIN [Briguori and Marenzi 2006] [Mueller 2006], many physicians still deny patients access to contrast media and consequently fail to generate critical and highly valuable diagnostic information. In addition, the safety of i.v. use of iodinated contrast media for CECT in patients with stage III or IV CKD has not been addressed in randomized controlled trials, and the existing controlled studies have been marred by the lack of randomization. As a result, it is unclear whether the risk of nephrotoxicity from the contrast medium outweighs the benefits of the information that would be obtained from the CECT. In this clinical trial, which will be a randomized placebo-controlled noninferiority study, GE Healthcare will assess renal safety of the i.v. administration of iso-osmolar iodixanol (Visipaque™ Injection 320 mg I/ml)

in patients who have stage III or IV CKD and are undergoing radiologic surveillance after an EVAR procedure. The randomization of patients to receive either CECT or an examination that does not involve contrast medium (nonenhanced computed tomography [NECT] plus non-contrast duplex ultrasonography) is justifiable because the relative value of the two approaches for post-EVAR surveillance cannot yet be made on the basis of the available evidence.

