The patients will be randomly assigned in a 1:1 ratio to undergo either CECT or NECT for this routine surveillance CT examination (full details are provided in the CT Imaging Manual). Patients in the CECT arm will receive a 100-mL i.v. injection of iodixanol (Visipaque Injection 320 mg I/mL), followed by a 10 mL saline flush, for enhancement of the CT examination. Patients in the NECT arm will receive a volume-matched i.v. injection of a saline placebo, followed by a 10 mL saline flush, before their CT examination. All patients (CECT and NECT arms) will be required to drink 500 mL of fluids following collection of blood samples for central analysis of SCr and prior to scanning. All patients (CECT and NECT arm) will be required to drink at least 2500 mL of fluids in the 24 hours immediately following CT scanning. To ensure a consistent approach, oral hydration is preferred, however, in case of concern about the patient's compliance and/or capability to follow the oral hydration instructions, i.v. administration of isotonic crystalloid solution (saline or bicarbonate) may be considered. In case of i.v. administration of crystalloids, the combination of oral and i.v. fluids must equal a minimum of 500 mL pre-contrast material administration and 2500 mL within 24 hours post-contrast material administration. Subjects will be asked to record their fluid intake. The volume of fluids, before and within 24 hours after administration, must be carefully documented in source records and in the CRF. Decision on use of i.v. hydration will be made and documented before randomization and implemented regardless of whether the subject is randomized to the NECT or CECT arm. The use of *N*-acetylcysteine (NAC) is discouraged for the purpose of preventing AKI.

To fulfil the ethical requirement for clinical equipoise, the patients in the NECT arm will undergo non-contrast duplex ultrasonography after their NECT imaging; ideally on the same day as the NECT imaging and within 2 days of performing the NECT. The purpose of the duplex ultrasonography is to detect vascular complications (e.g., endoleaks) that may not be visible in NECT images.

[figure not shown]
Images will be read at the site according to usual clinical practice to facilitate patient management decisions. The images obtained from the patients in both study arms will also be read in a central independent blinded read to assess imaging quality/diagnostic confidence.

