^g All blood samples taken prior to dosing and following the scan will be taken from venous blood. Local laboratories will be used for determination of eligibility for the trial and for stratification during randomization. A central laboratory will be utilized for analysis of SCr, cystatin C, and N-GAL collected at the Baseline Visit, Follow-Up 1 and Follow-Up 2 (for patients meeting primary AKIN criteria at Follow-Up 1). Sampling for Follow-Up 1 should occur as close to 48 hours as possible to support the primary endpoint assessment for AKI [ACR 2015], with use of the -6 hour window being preferable to use of the +6 hour window. Urine samples collected for NephroCheck® biomarkers (TIMP-2 and IGFBP-7) for patients where local NephroCheck® testing is available will be taken just before the scan, 4 hours post scan, and at 48 hours post scan.

^h Critical events, including EVAR-related post-baseline events, will be collected from administration to approximately 6 months after administration of Visipaque™ Injection/ saline placebo for assessment by the CEAC.

ⁱ 500 mL of fluids after SCr sampling and before the CT scan to be consumed. 2500 mL of fluids within the 24 hours post-CT period to be consumed. In case of concern about the patient's compliance and/or capability to follow the oral hydration instructions, i.v. administration of isotonic crystalloid solution (saline or bicarbonate) may be considered. Decision on use of i.v. hydration to be made and documented prior to randomization and performed regardless of whether the patient is randomized to the NECT or CECT arm.

^j CT scan according to correct acquisition protocol.

^k Non-contrast duplex ultrasonography will be performed ideally on the same day as NECT imaging and within 2 days of performing the NECT according to correct acquisition protocol.

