9.2 Baseline Visit

The Baseline visit will take place within 14 days of the Screening visit.

At the Baseline Visit, the following will be collected and/or performed:

Before administration of Visipaque™ 320 mgI/mL or saline placebo the following will be collected and/or performed:

- All female patients of child-bearing potential will undergo a urine pregnancy test.
- Inclusion/exclusion criteria will be checked.
- General medical/surgical history.
- Prior and concomitant medication.
- Physical examination.
- Vital signs (blood pressure, heart rate, respiration rate) in the sitting position.
- The patient will be randomized to the CECT arm or NECT arm by IWRS/IVRS.
- Blood samples will be drawn for laboratory evaluation (local clinical chemistry and hematology if not already done at screening and for central determination of SCr, cystatin C and N-GAL); see [Table 2](#).
- Urine sample for clinical chemistry (if not already done at screening), and Nephrocheck® biomarkers (where local NephroCheck® testing is available).
- The patient will receive oral hydration (500 mL of fluids) following collection of blood samples for central analysis of SCr. In case of concern about the patient's compliance and/or capability to follow the oral hydration instructions, i.v. administration of isotonic crystalloid solution (saline or bicarbonate) may be considered. Decision on use of i.v. hydration will be made and documented before randomization (to be implemented regardless of whether the subject is randomized to the NECT or CECT arm).
- Pre-treatment AEs, SAEs and critical events, including EVAR-related post-baseline events (from time of signing informed consent).

- Optional ORFM; for a subset of patients at selected sites, MB-102 will be administered 1 hour prior to Visipaque™ or saline placebo.

Administration of Visipaque™ 320 mgI/mL or saline placebo:

- Patients in the CECT arm will receive 100 mL of Visipaque™ Injection 320 mg I/mL followed by a 10 mL saline flush.
- Patients in the NECT arm will receive 100 mL of saline placebo, followed by a 10 mL saline flush.
- Study personnel must remain vigilant for the occurrence of AEs, particularly those that may be life-threatening. Personnel who are trained in the acute management of anaphylaxis and other emergencies and who have access to appropriate clinical supplies must be immediately available for 30 minutes after dosing.

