12.5 Study Treatments

For each administration of Visipaque or saline placebo, the volume administered will be summarized. Additionally, hydration pre-scan and within 24 hours post-scan will be summarized in terms of oral, i.v., and total volume of fluids.

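### In an open-label noninferiority trial, N-acetylcysteine to prevent AKI is only discouraged, so it could be started after randomization in contrast patients alone; i.v. hydration is protected by an arm-neutral rule that N-acetylcysteine lacks (minor)

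*Combined protocol and SAP*

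**What the plan says.** Section 8.4 states: "This study is not blinded". Section 9.2 lists, among the steps before administration at the Baseline Visit: "The patient will be randomized to the CECT arm or NECT arm by IWRS/IVRS". The site therefore knows the arm before the injection.

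On N-acetylcysteine, section 8.5 says only "NAC) is discouraged for the purpose of preventing AKI"; the synopsis and section 6.1 carry the same sentence. No exclusion criterion names the drug. The same paragraph of 8.5 uses binding language for other drugs: "the current use of i.v. vasopressor or inotropic medications is prohibited per exclusion criterion #14", and metformin, NSAIDs and nephrotoxic drugs have to be stopped for a time.

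I.v. hydration (saline or bicarbonate) is handled differently. Section 6.1: "Decision on use of i.v. hydration will be made and documented before randomization and implemented regardless of whether the subject is randomized". Table 1, footnote i: "Decision on use of i.v. hydration to be made and documented prior to randomization and performed regardless of whether the patient is randomized". The synopsis and the pre-administration list in 9.2 agree.

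On recording and analysis:
- Section 8.5 has medications entered in the eCRF with indication and dosage.
- Section 12.4 has concurrent medications coded and grouped by class.
- Section 12.1 splits all summary tables and listings by treatment group.
- Section 12.5 adds, beside the study-drug volume: "hydration pre-scan and within 24 hours post-scan will be summarized in terms of oral, i.v., and total volume of fluids".
- Section 12.6.4 adjusts the FAS sensitivity analysis for fluid intake only.

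**The concern.** Fear of contrast injury gives a clinician a reason to protect contrast patients and no matching reason to protect saline patients. The background section records the habit in general practice: "Even when rigorous hydration protocols and concomitant pre-medication are used in an attempt to prevent CIN", many physicians still withhold contrast. In an open-label trial, prophylaxis begun once the arm is known can fall in one arm only.

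If the drug reduces creatinine-defined AKI, one-arm use lowers P1 and leaves P2 unchanged. The observed P1 − P2 then understates the effect of contrast without prophylaxis, and the error is in the direction of the claim the trial is meant to support. Blinded adjudication and central-laboratory creatinine protect how the outcome is measured. They do not stop a co-intervention that changes the creatinine itself.

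The hydration rule shows that this route to bias was recognised and closed for one preventive measure but left open for another.

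**Working it through.** **Inputs from the protocol (12.6.2, 12.8):** P1 = P2 = 0.10 for planning, margin 0.05, one-sided 0.025, Miettinen–Nurminen score test, 80% power, 582 per arm (1164 in total), 1:1.

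**Step 1: reproduce the plan's figure.** The score-test formula is

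n = [(z₀.₉₇₅·s₀ + z₀.₈₀·s₁) / 0.05]²

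The rates constrained to the margin are 0.1303 and 0.0803.

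- s₀ = √(0.1303×0.8697 + 0.0803×0.9197) = 0.4326
- s₁ = √(2×0.10×0.90) = 0.4243
- n = [(1.960×0.4326 + 0.8416×0.4243) / 0.05]² = 580.7, so 581 per arm, against 582 in the plan

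Exact enumeration over both binomials, with variance factor N/(N−1), gives power 80.5% at 582 per arm. The plan's figure is reproduced.

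**Step 2: error at the margin without any prophylactic drug.** With P1 = 0.15 and P2 = 0.10, the same enumeration gives a false-noninferiority probability of 2.47%.

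**Step 3: one-arm use.** The documents give neither uptake nor effect, so both are assumptions here. Let a share f of CECT patients only receive a drug that lowers their AKI risk by r. Then P1 = 0.15 − f×r and P2 = 0.10. Full effect means that the whole 5-point excess is removed in users (r = 0.05); half effect means r = 0.025.

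| f (patients of 582) | P1, full | error, full | P1, half | error, half |
|---|---|---|---|---|
| 0 | 0.1500 | 2.5% | 0.1500 | 2.5% |
| 2% (12) | 0.1490 | 2.8% | 0.1495 | 2.6% |
| 5% (29) | 0.1475 | 3.3% | 0.14875 | 2.9% |
| 10% (58) | 0.1450 | 4.4% | 0.1475 | 3.3% |
| 20% (116) | 0.1400 | 7.5% | 0.1450 | 4.4% |

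The error reaches 5% at about 72 CECT users (12.3%) with full effect, or about 143 (24.7%) with half effect. If r = 0 it stays at 2.5% for any uptake.

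**Step 4: a different effect model.** If the drug cuts all AKI in users by a relative amount ρ, P1 = 0.15(1 − f×ρ). At f = 10% and 20% the error is 3.5% and 4.9% for ρ = 20%, 4.2% and 6.7% for ρ = 30%, and 5.8% and 12.0% for ρ = 50%.

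**Step 5: the same use in both arms.** This tests whether arm-neutral use would be enough.

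- A drug that cuts all AKI by one third in users gives P1 = 0.15(1 − f/3) and P2 = 0.10(1 − f/3). The error is 2.7%, 3.0% and 3.7% at f = 5%, 10% and 20%. The matching one-arm figures are 3.3%, 4.4% and 7.5%, because one third of 0.15 is 0.05.
- A drug that acts only on the contrast excess leaves P2 at 0.10. The error is then the same as in the full-effect column: 3.3%, 4.4% and 7.5%.

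Arm-neutral use therefore removes selection by arm. It does not remove dilution by a drug that works only against contrast injury.

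**The case against.** The strongest case for leaving the text alone has five parts.

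- **The wording was chosen.** Amendment A04 added the sentence to address this drug, and discouraging it was a decision. That stands: the text contains no contradiction or error. It is still weaker than the hydration rule.
- **A site that gave the drug would be acting against guidance.** A reader might infer that a site could follow the protocol to the letter and give the drug in one arm. The documents do not support that. Such a site disregards stated advice, though it breaks no rule.
- **The window is narrow.** The arm is assigned at the Baseline Visit, so pre-medication begun before then cannot depend on it. Only a drug started between allocation and the Follow-up 1 sample can be selective. The background remark concerns general practice and says nothing about use in this trial. Both points stand, and both limit the likely uptake.
- **Use would be visible.** Indication is recorded, concurrent medications are summarized and tables are split by arm. A reader might infer from 12.5 and 12.6.4 that imbalance would go unseen; sections 8.5, 12.1 and 12.4 show otherwise. Visibility is not prevention, however.
- **The size rests on assumption.** At 2% to 5% uptake the illustrated error is only 2.6% to 3.3%, and whether the drug affects creatinine-defined AKI cannot be settled from the documents. This stands in full and is why the point is minor.

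Sections 12.6.3 and 12.10 also defer some handling to a SAP. Its treatment of such use could not be checked, but an analysis rule could not stop the use.

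**Conclusion.** The point holds in a limited form. The wording permits, against advice, prophylaxis started after allocation in contrast patients alone, while i.v. hydration is protected from this. If the drug lowers creatinine-defined AKI, the bias is toward noninferiority.

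The size is unknown. At true rates of 15% and 10% with full removal of the excess in users, the error goes from 2.5% to 3.3% at 5% uptake and 4.4% at 10%. It stays at 2.5% if the drug has no effect, and changes little if use is rare. Uptake, effect and the 15% rate are assumptions for illustration.

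A reader might go further and infer that the trial's result is biased, or that sites gave the drug selectively. The documents show what is permitted and contain no evidence of use, so neither inference is supported. Priority: minor.

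**What to change.** In the synopsis, 6.1 and 8.5, replace the sentence with wording to this effect:

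*N-acetylcysteine, or any other drug given in order to prevent AKI, must not be started between randomization and the Follow-up 1 blood sample; saline or bicarbonate under the hydration rule is excepted. Where local practice requires such a drug, the decision must be taken and documented ahead of randomization and carried out in whichever arm is assigned.*

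The exception should stay narrow: it removes selection by arm but not dilution by a drug that acts only on the contrast excess (step 5).

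Report such use by arm, next to hydration in 12.5, from the concomitant-medication data already collected. No new eCRF item is needed, and the FAS stays primary.

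**Cost:** one sentence in three places and one table line. Investigators lose a little discretion over a drug the protocol already discourages; required hydration in both arms is unaffected. Use against the rule becomes a protocol deviation under 13.3, handled by the existing per-protocol definition in 12.3.3. Patients who received the drug would remain in the FAS, so the rule reduces the risk but cannot guarantee its absence.
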